11.4 Safety evaluation

Data from all subjects who receive any study drug will be included in the safety analyses. Subjects who entered the study and did not take any of the study drugs and had this confirmed, will not be evaluated for safety.

The severity of the toxicities will be graded according to the NCI CTCAE v4.0 whenever possible.

11.5 Sample Procurement for Immunologic Assessment

If a patient has consented and agreed to allow their blood to be used for research studies, 7-10 mL of whole blood in one purple top tube, 8mL in one BD vacutaner CPT cell preparation tube, and 7-10 mL in a serum separator tube will be acquired at the following timepoints: prior to treatment, and at day 15, 30, 60, and 120 and at the completion of treatment. Samples will be held on ice, centrifuged at 2500 RPM for 10 min, separated as soon as possible, and aliquoted into one (Preferably two) vials containing 0.1 – 0.5 mL serum each and two vials with the cellular contents. The cellular material obtained from the CPT tubes by removing the top layer (according to the manufacturers recommendations) and will be mixed with an equal part of freezing solution (30% DMSO + 70% fetal calf serum). The tubes will be labeled with a nonpatient identifying ID number with the date of collection, protocol number, and source and intended use of the material (i.e., plasma sample for cytokine assays). Sample volumes between 0.05 and 0.1 mL are acceptable, but the laboratory will not be able to repeat the analysis or further dilute the sample, if necessary. Samples will be frozen at -70°C batched and archived. Immune assessment will be done as described below. If there are any questions with sample procurement please page the study PI ([name])

11.6 CORRELATIVE STUDIES.

In this Phase II clinical trial the immunological affects of the combination of Lenalidomide and Rituximab in patients with previously untreated indolent NHL will be explored.

Rationale:

This clinical study will be a unique opportunity to measure and characterize the baseline immune parameters and immune modulating effects of lenalidomide with or without rituximab in patients with previously untreated indolent NHL. This will allow for a better understanding of the mechanism of action, better prediction of who will respond to treatment, and allow for rational design of future clinical trials with these and/or other biologics.

Objectives:

Comprehensive assessment of immune parameters prior to therapy, after treatment with lenalidomide alone, and after treatment with the combination of lenalidomide and rituximab

Assay timeline:

Baseline, day + 15, +30, +60, and +120, completion of study, progression or withdrawal. Additional blood draws for immunologic profiling for patients taking part in the additional radiation therapy cohort will be done at day 15, 30 after starting radiation therapy and at the

time of progression. If the patient progresses within 8 weeks, the blood draw at progression will not be done.

Given that the protocol requires 2 weeks of lenalidomide alone followed by rituximab, this will allow for assessment of immune parameters at baseline, after treatment with lenalidomide alone, and after combination therapy with lenalidomide and rituximab. Because there have been dramatic responses to lenalidomide alone in the first cohort of patients on the relapsed protocol immune profiling patients before and after rituximab is added is justified.

Methods:

Distribution, phenotype, and frequency of mononuclear cell subsets: To examine the overall pattern of mononuclear cell subsets, blood will be collected from patients (see Study Calendar) prior to, during and after therapy. After preparation via standard procedures, the cells will be analyzed using a multi-parameter, Hi-D FACS to determine the frequency and phenotype of mononuclear subsets including: helper T cells, cytotoxic T cells, regulatory T cells, naive T cells, memory T cells, NKT cells, NK cells, dendritic cell subsets and B-cell subsets, Table 1.

Assay of T Cell Proliferation, Cytokine Production and Cytotoxic Lymphocyte (CTL) Activity: CD4 and CD8 T cells will be purified from blood using EasySep (Stem cell Technologies; Vancouver, BC, Canada). Cells (1x10⁵/well in 200 μL culture media) will be cultured in quadruplicate 96-well U-bottom plates for each condition: culture medium alone or medium supplemented with CD3/CD28 mAb (0.5 μg/ml), or PHA (5 μg/ml). Cells will be incubated for 3-5 days at 37°C, 5% CO₂. Sixteen hours before the end of the incubation, 1 μCi of [³H] thymidine will be added per well. Following harvest of cells, [³H] thymidine incorporation will be measured with a beta counter following dissolution in scintillation fluid.

The culture supernatants will be collected prior to addition of [3 H] thymidine and stored at -70°C. The supernatants will be assayed for several cytokines/chemokines (e.g. IL-2, IFN- γ , IL-17, IL-10, IL-4, TNF- α , TGF- β) using the Multiplex Bead-based Luminex® Technology, Cytokine Human 10-Plex Panel (or if batched with other samples, the Cytokine Human 25-Plex Panel) (Invitrogen, Carlsbad, CA), see below.

CTL activity will be assessed by using the ELISpot Assay Kit (R&D Systems, Minneapolis, MN) by measuring IFN-gamma producing CD8+T cells, per the manufacturer's recommendations.

Table 1: Phenotypic markers for analysis of various immune cells

Cell subset		Phenotype marker
T cell	CD4 ⁺ helper T cell	CD3 ⁺ CD4 ⁺
	CD8 ⁺ cytotoxic T cell	CD3 ⁺ CD8 ⁺
	Regulatory T cells	CD3 ⁺ CD4 ⁺ CD25 ⁺ Foxp3 ⁺
	Naïve T cell	CD4 ⁺ /CD8 ⁺ CD45RA ⁺ CD11a ⁺
	Memory T cell	CD4 ⁺ /CD8 ⁺ CD45RO ⁺ CD11a ⁺
	NK T cell	CD3 ⁺ CD56 ⁺ CD16 ⁺
	iNKT cell	CD3 ⁺ CD56 ⁺ CD16 ⁺ 6B11 ⁺ CD1d ⁺
NK cell		CD3 ⁻ CD56 ⁺ CD16 ⁺
B cell	B2 cell	CD19 ⁺ IgD ⁺ CD11b ⁻ CD5 ⁻
	B1a cell	CD19 ⁺ IgM ⁺ CD11b ⁺ CD5 ⁺
	B1b cell	CD19 ⁺ IgM ⁺ CD11b ⁺ CD5 ⁻
Dendritic cell	Myeloid DC	CD11c ⁺ HLADR ⁺ lymphomononuclear cell
		lineage negative
	Plasmacytoid DC (pDC)	CD123 ⁺ BCDA2/BCDA4 ⁺ HLADR ⁺
		lymphomononuclear cell lineage negative

T-reg Cells Function: CD4⁺CD25⁺ FoxP3⁺T cells will be isolated using magnetic separation with the MACS CD4⁺CD25⁺ isolation kit (Miltenyi Biotec, Auburn, CA) and then cultured with CD4⁺CD25⁻T cells in plates coated with anti-CD3/CD28 antibodies (5 µg/ml each) in the presence of Lenalidomide, or saline (control) for 3 days. The supernatant will be collected before the addition of [³H] thymidine for measurement IL-10, IL-4, TGF-β, IL-2, TNF-α, and IFN-γ by multi-parameter Hi-D FACS analyses or Multiplex Bead-based Luminex® Technology. Proliferation will be measured after 72h in culture, with [³H] thymidine labeling for the last 16 hours.

Multiplex Bead-based Luminex® Technology: The microbead multiplex detection system developed by Invitrogen) enables detection of numerous cytokines simultaneously in a single reaction container [39]. In this technology, molecular reactions take place on the surface of microscopic plastic beads (2 um). For each reaction, capture molecules (i.e., mono-specific antibodies) are covalently attached to the surface of internally color-coded microbeads. The assigned color-code identifies the reaction in a specific microbead population throughout the test. Multiplex capability involves mixing several populations of microbeads, each with a specific capture molecule, into one reaction vessel at the start of the test. The magnitude of the biomolecular reaction is measured using a reporter molecule which signals the extent of the reaction by attaching to the test molecules captured on the microbeads. To perform a test, the color-coded microbeads, reporter molecules, and sample (e.g., tumor cell lysate) are mixed and then injected into the Luminex flow cytometer where lasers illuminate the colors inside and on the surface of each microbead. This method is rapid, sensitive, and quantitative, and lends itself to high-throughput in an economical fashion [40].

Serum Cytokines: The Luminex assay for immunologic analytes will include 37 different cytokines and growth factors (including IL-1, 2, 4, 5, 6, 7, 10,12, 17, TNF, INF-γ, TGF-beta, GM-CSF, PDGF, and VEGF) (Invitrogen). This test will allow for the ultrasensitive

determination of cytokines in the serum of patients before and during Lenalidomide alone and Lenalidomide in combination with Rituximab.

B-cell Phenotype and Functional Analysis: The B-cell phenotype will also be assessed. Blood mononuclear cells will be prepared with EasySep and stained with antibodies (Zymed, San Francisco, CA) against each set of markers listed in Table 1. Clearly B-cells in these patients are going to be radically different at different stages of the protocol, because the patients will have been on rituximab, which depletes B-cells. This will give us an opportunity to assess Lenalidomide's function before and after rituximab in the same patients. The phenotype of B-cell subsets (Table 1) will be analyzed by FACS.

A B cell functional assay will be performed by measuring IgM production using B cells isolated from blood. CD19⁺ B cells will be isolated by positive selection using magnetic beads (2). B cell subsets will be sorted by FACS. B cell will be stimulated by LPS or CpG for 3 days, then IgM production will be measured by ELISA [41].

Immunoglobulin Levels: Serum samples will be obtained at various time points to assess for the serum levels of IgM, IgA, and IgG. Immunoglobulin levels will be measured by the clinical lab at UCDMC using standard techniques.

NK, NKT and iNKT cell phenotype and functional assay: Human iNKT cells will be identified using CD1d tetramer and a novel monoclonal antibody (clone 6B11) specific for the CDR3 loop of the human $V\alpha24J\alpha18$ TCR alpha chain which specifically identify iNKT cells. Other antibodies comprise CD3-APC, CD4-PerCP and CD8 α -FITC (BD Biosciences, San Jose, CA). For surface staining, cells will be washed with staining buffer (PBS with 2% FCS), and incubated for 30 minutes, on ice in the dark with the relevant antibody combinations. Cells will then be washed twice with staining buffer and analyzed by flow cytometry (BD Coulter). Data will be collected using a FACS ARIA (BD Biosciences) and analyzed by "Flowjo" flow cytometry data analysis software (Tree Star Inc, Ashland, OR).

NK (CD3-CD56+CD16+), NKT (CD3+CD56+CD16+) and iNKT cells will be sorted from blood. The sorted NK/NKT cells will be stimulated with poly IC for 12 and 24 h. iNKT cells will be stimulated with iNKT cell-specific ligand, α-GalCer. Supernatants will be collected to analyze the levels of IFN-gamma, IL-6 and IL-8 using the BD cytometric bead array kit per the manufacturer's recommendations. IFN-gamma and IL-4 will be measured by CBA kit or intracellular staining. Sera cytokine will be measured by CBA kit.

NK Cell Killing Activity: NK cells bind to, and kill K562 cells (a human myelogenous cell line, ATCC) thus forming the basis of this functional killing assay [42]; this flow cytometric assay can detect binding and killing. K562 cells will be grown in RPMI 1640 with 10% fetal calf serum and checked for viability by trypan blue exclusion before use. Sorted NK cells that are obtained before and after treatment initiation will be combined with K562 cells at an effector-target-cell ratio of 20:1. Incubation will proceed for up to 3 hours at 37°C in 5% CO₂. NK cells will be tested for their killing activity with or without stimulation by IL-2 (1 ng/ml of human rIL-2; Genzyme, Cambridge MA). Spontaneous lysis will be tested at each time point using equivalently cultured K562 cells in the absence of effectors. If we encounter any problems with this assay, a standard ⁵¹Cr-release assay will be done, testing groups equivalent

to those described above. NK cells will also be assessed for Rituximab-mediated ADCC by using the human NHL cell line Raji (ATCC) as the target cell. The assay will be done as described above with and without 50ug/ml of Rituximab added.

Response of PBMC to Stimulation with Tetanus Toxoid and Tetanus Specific Antibody Production: The response to tetanus toxoid or PPD will be used to assess the immune response of patients on the study. As in the general population, the patients in this study will have been vaccinated against tetanus at some point in their lives. The response to tetanus toxoid does vary between people with a number of factors such as age, steroid use and other random factors [43, 44], however that is not a problem in this study since pre-study values will act as an internal control. As similar to the other assays assessment will be at baseline and after the first and fourth cycle.

Cellular Proliferation Response to Tetanus Toxoid: The *in vitro* cellular proliferative response will be measured as previously described [43, 44]. Using standard isolation techniques, PBMC (1×10^5) in $100~\mu$ L RPMI 1640 (10% human AB+ sera) will be cultured in 96-well round bottom microtiter plates, in triplicate with either tetanus toxoid ($10~\mu$ g/ml, Massachusetts Public Health Biological Laboratories; Cambridge, MA) or PPD ($10~\mu$ g/ml Statens Serum Institute). Phytohemagglutinin (PHA) will be the positive control, and unstimulated cells will be the negative control. Cultures will proceed for 5 days at 37% C and 5% CO₂, then pulsed with $1~\mu$ Ci/well of 3 H-thymidine for 18~hours. Cells will then be harvested; tritiated thymidine uptake determined and reported as the proliferation index.

Antibody Response to Tetanus Toxoid: Tetanus toxoid-specific antibodies will be determined using ELISA as previously described [44]. PBMC from patients will be cultured with tetanus toxoid for 7 days as described above, and then the supernatant from the wells will be harvested. Microtiter plates (96-well) will be coated with tetanus toxoid (2 µg/ml) overnight at 4°C, then washed and blocked with 1% human serum albumin in 0.05 M carbonate buffer. Then serum samples obtained from patients (100 µl) will be added to the wells and incubated for 120 minutes, then washed. Biotinylated goat anti-human IgG or IgM (Zymed) will be diluted and added to the wells. Subsequently, streptavidin-conjugated alkaline phosphatase (Zymed) will be added along with the color substrate (Bio-Rad, Hercules, CA). Optical density will be read at 405 nm in an automatic plate reader.

Monocyte Activation: Monocytes play a critical role in immunity, antigen presentation and regulation. CD80 (B7.1), HLA-DR and TNF- α secretion are markers of monocyte activation. Their activation status will be tested. Monocytes will be obtained and cultured as described previously [45], with or without LPS (1 µg/ml E. coli 055:B5, Sigma, St. Louis, Mo). Cells will be incubated with fluorescein isothiocyanate-conjugated anti-CD80 or anti-HLA-DR (Pharmingen, San Diego, CA) and subjected to FACS for analysis. The secretion of TNF- α will be done by using with the Multiplex Bead-based Luminex system, see above. Samples for TNF- α may be frozen and stored for batch analysis.

RNA sequence analysis: When available, protocol required biopsy material (formalin fixed paraffin embedded or fresh frozen) either at the time of diagnosis, study enrollment, or at relapse will be labeled with a non-patient indemnifying ID number with the date of collection,

protocol number, and source. This material will be provided to Celgene along with relevant non-patient indemnifying clinical data for complete mRNA sequence analysis (RNA SEQ) and will be statistically correlated with clinical outcome. The unused biopsy material will be subsequently returned to UC Davis Medical Center Department of Pathology.

Biopsy specimens will be sent to:

[name].

Senior Director

Translational Development & Diagnostics

Celgene Corporation

Return unused biopsy material to:

UC Davis Medical Center Department of Pathology

Statistical Analysis: Statistical analysis of lymphocyte frequency and functions between the groups will be done by unpaired Student's t test. The study design proposed will be interpreted by [name], Division of Biostatistics, University of California, Davis.

12 Regulatory Considerations

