5.1.2 Secondary study objectives

- Time to disease progression, safety, tolerability, duration of response, and overall survival.
- To assess changes in serum cytokines as well as cellular immune phenotypic and functional changes before and after treatment, and correlate these changes with response.
- Examine immune correlates after local radiotherapy

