6.1 Treatment Schedule

Lenalidomide capsules will be taken orally in the morning each day on days 1 - 21, followed by 7 days of no therapy of each 28-day cycle. Rituximab will be given by intravenous infusion weekly for 4 weeks beginning on day 15 of treatment start, thus on days 15, 22 of cycle 1 and days 1 and 8 of cycle 2.

Following cycle one, therapy with lenalidomide will continue in 28-day cycles, until there is disease progression, unacceptable toxicity or the patient chooses to withdraw from therapy. Lenalidomide may be discontinued after twelve cycles if complete response demonstrated, per physician and patient discretion. Additional course of rituximab will be administered if CR not attained after cycle 4, to be administered during cycle 5 on days 1, 8, 15 and 22. The patient must see the study physician before the next cycle may begin. There will be a +/-3 day window for study visits and procedures after completion of cycle one.

Dosing regimen

The planned maximum dose of lenalidomide for investigation is 20 mg daily, days 1-21 of a 28 day cycle. Dosing will be in the morning at approximately the same time each day. Lenalidomide may be taken orally either with a full or an empty stomach.

Due to the uncertain amount of re-absorption of lenalidomide, there will be no re-dose for lenalidomide if the patient vomits the pills.

Lenalidomide capsules should be swallowed whole, and should not be broken, chewed or opened.

If a dose of lenalidomide is missed, it should be taken as soon as possible on the same day. If it is missed for the entire day, it should not be made up.

Patients who take more than the prescribed dose of lenalidomide should be instructed to seek emergency medical care if needed and contact study staff immediately.

Prophylactic anti-coagulation is required during lenalidomide treatment. See Section 6.5.1.2.

Rituximab 375 mg/m2/week will be administered by IV infusion starting on day 15 from start of treatment and will continue weekly for 4 weeks (a total of four doses). The course of rituximab will be repeated if CR not attained after cycle 4. It will be administered at 375 mg/m2 weekly during cycle 5 on days 1, 8, 15 and 22.

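### The day-120 immune sample falls inside a second rituximab course given only to patients without CR, so at that time point response is mixed with re-treatment

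*Combined protocol and SAP*

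**What the plan says.** Section 11.5 fixes the immune draws by calendar day: "prior to treatment, and at day 15, 30, 60, and 120 and at the completion of treatment". The synopsis and footnote 10 of the schedule give the same days. The assay timeline in section 11.6 writes them as offsets: "Baseline, day + 15, +30, +60, and +120, completion of study, progression or withdrawal".

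Treatment runs by cycle. In section 6.1 lenalidomide is taken "on days 1 - 21, followed by 7 days of no therapy of each 28-day cycle", and the first rituximab course is given weekly from day 15, "thus on days 15, 22 of cycle 1 and days 1 and 8 of cycle 2". The same section adds: "Additional course of rituximab will be administered if CR not attained after cycle 4". That second course is on days 1, 8, 15 and 22 of cycle 5.

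The samples serve two purposes. Section 5.1.2 plans to assess immune changes "before and after treatment, and correlate these changes with response". Section 11.6 relies on the two-week lenalidomide lead-in and says "this will allow for assessment of immune parameters at baseline, after treatment with lenalidomide alone, and after combination therapy with lenalidomide and rituximab". The tetanus paragraph in 11.6 gives a cycle-based timing: "As similar to the other assays assessment will be at baseline and after the first and fourth cycle". For the cellular data, 11.6 names one test, an unpaired t test between groups that it does not define.

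**The concern.** Draws are set by calendar day, while drug exposure is set by cycle day and, from cycle 5, by response. Where the two meet, an immune difference between response groups may come from the treatment rule and not from the biology the objective is about.

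At day 120 the rule itself sends non-CR patients to further rituximab and leaves CR patients without it. A difference in, say, NK activity, ADCC or cytokines could arise from re-treatment alone and be reported as a correlate of response. Such a finding could then inform prediction of response and the design of later trials, which section 11.6 gives as reasons for the work.

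A separate and smaller matter is whether the samples isolate lenalidomide alone from the combination. That depends on whether the day-15 sample precedes the first infusion, and on how comparable the later samples are in lenalidomide phase.

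**Working it through.** **Inputs.** 28-day cycles, lenalidomide on days 1–21, first rituximab course weekly ×4 from day 15, second course on cycle 5 days 1, 8, 15 and 22 if not in CR (section 6.1). Draw days come from 11.5 and 11.6. The ±3 day window outside screening and cycle 1 is in the notes to the schedule. Delay of a new cycle for toxicity is in 6.4.2.

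**Formula.** With the first dose on day 1, cycle = floor((d − 1)/28) + 1 and cycle day = ((d − 1) mod 28) + 1.

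**The plan's own figure.** Weekly ×4 from day 15 gives study days 15, 22, 29 and 36, that is cycle 1 days 15 and 22 and cycle 2 days 1 and 8. This matches section 6.1.

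**Second course.** Cycle 5 day 1 is 4 × 28 + 1 = day 113, so the doses fall on days 113, 120, 127 and 134.

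**Draws mapped to the regimen (on schedule):**

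| Draw | Cycle/day | Consecutive lenalidomide doses, including that day | First-course doses on earlier days | Second-course doses on earlier days, non-CR |
|---|---|---|---|---|
| 15 | C1D15 | 15 | 0 (dose 1 is due that day) | 0 |
| 30 | C2D2 | 2 | 3 of 4 | 0 |
| 60 | C3D4 | 4 | 4 of 4 | 0 |
| 120 | C5D8 | 8 | 4 of 4 | 1 (dose 2 is due that day) |

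**Time since last rituximab at day 120.** In CR patients it is 120 − 36 = 84 days. In non-CR patients it is 120 − 113 = 7 days if the sample precedes that day's infusion, and 0 if it follows.

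**Window.** Days 117–123 lie wholly within days 113–134 and exclude cycle 5 day 1. Read as an offset, day +120 is day 121, after two second-course doses.

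**Delays.** With 7 days of cumulative delay, day 120 is C5D1; with 14 days it is C4D22. A fixed calendar day therefore falls at different points of the regimen in different patients.

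**Comparison by objective response (CR + PR).** PR patients are also re-treated, so the overlap is partial. The documents give no rates at cycle 4. Taking the cited rates from other studies as assumptions:
- 31% CR and 44% PR (relapsed disease): 44/75 = 59% of responders re-treated.
- 86% overall and 75% CR (front-line): 11/86 = 13% of responders re-treated.

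**Number re-treated, same assumptions.** 30 × (1 − 0.75) = 7.5 and 30 × (1 − 0.31) = 20.7, so roughly 8 to 21 of 30. This holds only if every patient consents to sampling and is still on treatment at day 120.

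**Alternative draw.** At cycle 5 day 1 before infusion, no patient has had a second-course dose, and on schedule the last first-course dose was 113 − 36 = 77 days earlier in everyone.

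**The case against.** The best reply is that the plan keeps clean time points. Day 60 follows all four first-course doses, comes 24 days after the last one, and precedes any second-course dose. Baseline, day 15 and day 60 can therefore serve both objectives. This stands. A reader might infer that both correlative objectives are lost, and the documents do not support that. What remains is a phase mismatch: about 14–15 consecutive lenalidomide doses at day 15 against 4 at day 60.

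Other strong readings also fail.

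- **That lenalidomide is absent at day 30.** The rest week is 168 h, or 56 half-lives at the 3 h stated in 5.3.1.2. But dosing restarted on day 29, and that section reports no accumulation. A 24 h dosing interval is already 8 half-lives, so plasma exposure at day 15 also comes from the most recent doses. Any difference would lie in the duration of immune effect, for which no figure is given. Day 30 has the same planned phase in all patients, so it does not confound the response correlation.
- **That CR patients are rituximab-free at day 120.** 84 days is 2016 h, or 11.6 half-lives at 174 h. Section 5.3.2.2, however, says rituximab stays detectable for 3–6 months, with B-cell recovery from about 6 months. The contrast is recent re-treatment against none, and B-cell subsets are a poor example of it.
- **That response and re-treatment are one variable.** PR patients are re-treated too.
- **That the tetanus timing contradicts the draw days.** Cycles 1 and 4 end on days 28 and 112, and days 30 and 120 do come after them. The wording needs aligning, but it is not a clear conflict.

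Pre-infusion intent at day 15 can fairly be read from 11.6, which treats that sample as lenalidomide alone. It is still not stated, and an offset reading puts the sample on day 16, after the first infusion.

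Finally, this work is exploratory. That limits the consequence, but it does not remove the bias at day 120.

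**Conclusion.** The point holds for day 120. For CR against non-CR, the sample mixes response with recent rituximab by protocol rule: 7 days or less since the last dose against 84 days. For objective response the mixing is partial. No analysis in the plan separates them.

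Day 30 is only a weak contrast of lenalidomide alone with the combination: three of four rituximab doses given, and the second lenalidomide dose after the rest week. Day 60 is usable for both objectives, as is day 15 if drawn before the infusion.

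This rests on on-schedule cycles, on day 1 being the first dose, and on the response correlation being run at day 120, which the plan neither requires nor rules out. The size of any bias in an immune measure cannot be computed from the documents. The primary endpoint is not affected, so this is worth correcting but does not threaten the main result.

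**What to change.** Changes to sampling and analysis only:

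- Take the day-120 sample at the existing cycle 5 day 1 visit, before any second-course infusion. Planned rituximab exposure is then the same in every patient. The sample follows the rest week (days 106–112) in everyone, so it serves the response correlation and not the lenalidomide-phase contrast.
- State that the day-15 sample is drawn before the first rituximab infusion.
- Align the synopsis, 11.5, 11.6, footnote 10 and the schedule table on one set of times, and say whether a day is a study day or an offset.
- For samples already stored at day 120, make no CR versus non-CR comparison and show results by second-course status. Use change from baseline to day 60 as the last on-treatment correlation with response at common planned rituximab exposure.

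Day 30 need not move for the response correlation. Moving it to cycle 2 day 8 is a debatable trade: about 7 consecutive lenalidomide doses against 14 before a pre-infusion day-15 sample, with the first rituximab course still unfinished.

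The cost is a wording amendment, with the same number of draws at existing visits. The downside is that stored day-120 samples are not interchangeable with new cycle 5 day 1 samples, so the two must be reported separately.

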5.3.2.1 CLINICAL PHARMACOLOGY

Mechanism of Action:

Rituximab binds to the antigen on the cell surface, activating complement-dependent cytotoxicity; and to human Fc receptors, mediating cell killing through an antibody-dependent cellular toxicity.

5.3.2.2 Pharmacokinetics and Drug Metabolism:

Absorption:

Rituximab is administered intravenously.

Pharmacokinetic Parameters:

Metabolism and Excretion:

Rituximab remains detectable in the serum for 3-6 months after completion of treatment with B-cell recovery beginning about 6 months following completion of treatment. Median B-cell levels return to normal by 12 months after completion of therapy. Once infused, absorption is

immediate and results in rapid and sustained depletion of circulating and tissue-based B cells. The half-life of rituximab at doses >100 mg/m2 is 4.4 days (range of 1.6-10.5 days). At doses of 375 mg/m2, the half life is 50 hours following the first dose to 174 hours following the fourth dose). The mechanism of clearance for rituximab is uncertain although phagocytosis and catabolism in the reticuloendothelial system is suspected.

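### The tetanus-antibody assay harvests culture supernatant but loads patient serum into the ELISA, so as written it reads circulating antibody and not antibody made by the stimulated cells

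*Combined protocol and SAP*

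**What the plan says.** Section 11.6 introduces the tetanus block as "Response of PBMC to Stimulation with Tetanus Toxoid and Tetanus Specific Antibody Production". It states that "the patients in this study will have been vaccinated against tetanus at some point in their lives" and makes each patient's pre-study value the internal control. It places the assessments at baseline and after cycles 1 and 4.

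The antibody paragraph defers to a cited method and then sets out the steps. First, "PBMC from patients will be cultured with tetanus toxoid for 7 days as described above, and then the supernatant from the wells will be harvested". Plates are then coated with tetanus toxoid and blocked. The next step is "Then serum samples obtained from patients (100 µl) will be added to the wells and incubated for 120 minutes, then washed". Labelled anti-human IgG or IgM, substrate and a plate reading at 405 nm follow.

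Serum is available for this. Under section 11.5, "7-10 mL in a serum separator tube will be acquired at the following timepoints", and those times are pre-treatment, days 15, 30, 60 and 120, and completion. The assay timeline in section 11.6 gives the same days and adds progression or withdrawal.

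On rituximab, section 5.3.2.2 describes rapid and sustained loss of B cells, with "B-cell recovery beginning about 6 months following completion of treatment".

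**The concern.** The specimen prepared for the assay is not the specimen tested. Antibody in the supernatant of a stimulated culture reflects what the patient's cells can do at that visit. Antibody in serum is a standing level that earlier vaccination can sustain whatever those cells can do. The two can move differently, most obviously under a B-cell-depleting drug.

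A secondary objective (section 5.1.2) is to assess functional immune change from before to after treatment and to relate it to response. A serum titre entered there as a functional measure would be the wrong quantity for that purpose. A laboratory could carry out the sentence exactly as printed, because serum tubes are drawn, so nothing in the workflow would expose the mismatch.

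**Working it through.** The main check follows each specimen through the text. The only arithmetic concerns sampling times.

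**1. Specimen trace (section 11.6, Antibody Response to Tetanus Toxoid)**
- PBMC + tetanus toxoid, 7 days → supernatant harvested → no further step.
- Patient serum, 100 µl → toxoid-coated wells → anti-IgG/IgM → optical density.

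The optical density is a function of the serum only.

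**2. Is the supernatant used elsewhere?** The other supernatants assayed in section 11.6 come from the T-cell, regulatory T-cell and NK/NKT/iNKT cultures and are tested for cytokines. The B-cell functional assay measures IgM after LPS or CpG stimulation. None uses the tetanus culture, so no other paragraph repairs the gap.

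**3. Does the internal control rescue it?** The within-patient contrast is serum reading at time t minus serum reading at baseline. That tracks change in circulating titre. The culture appears in neither term.

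**4. Culture conditions.** The antibody paragraph points back to the culture described above it. That culture (Cellular Proliferation Response) runs 5 days followed by an 18-hour pulse, not 7 days, and its medium contains 10% human AB+ serum. If that donor serum carries anti-tetanus antibody (an assumption; the documents do not say), supernatant would show a signal that the patient's cells did not make. The antibody paragraph names no controls of its own.

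**5. Sampling times.** With 28-day cycles and no delays, day 1 of cycle c is 28 × (c − 1) + 1.
- After cycle 1: day 29. After cycle 4: day 113.
- First rituximab course (section 6.1): days 15, 22, 28 + 1 = 29 and 28 + 8 = 36.
- Day 29 therefore follows two doses and precedes the day-36 dose.
- Day 113 is 113 − 36 = 77 days after the last first-course dose. Day 120, the nearest day in the general timeline, is 120 − 36 = 84 days after it.
- A second course ends on day 22 of cycle 5: 4 × 28 + 22 = day 134.
- An end-of-treatment sample after 12 cycles (12 × 28 = day 336) is 336 − 36 = 300 days after a first course, or 336 − 134 = 202 days after a second.

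Taking 6 months as about 180 days, days 113 and 120 fall before B-cell recovery is expected to begin. Day 336 falls after it. Day 15, which section 11.6 treats as the end of lenalidomide alone, is in the general timeline but not among the times named for this assay.

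**6. Number of readings.** 30 patients × 3 times (baseline, after cycles 1 and 4) = 90. This is a ceiling, because sampling depends on consent.

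**The case against.** The best counter-argument is that the intended specimen is not known. The method rests on a cited source that cannot be checked here. Serum is drawn at every time. The block's title joins cell response and antibody production with a plain conjunction, and a serum titre against baseline fits the general aim of assessing patients' immune response. The word for serum may be a slip for supernatant, the culture step may be left over, or two readouts may have been merged. This stands. It limits the claim to what the text does as printed, and it means the fix must offer alternatives. It does not remove the mismatch, because the culture has no stated purpose under a serum-only reading.

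A reader might infer more than the documents support in two ways.
- *That every reading is from the wrong specimen and will be reported as preserved immune function.* The documents do not say how the result would be reported. Serum titre is a valid quantity, only a different one from cellular antibody production.
- *That no post-baseline time could show a lenalidomide effect, because both fall at most 77 days after rituximab.* The 77 days apply to day 113 only; day 29 comes before the last first-course dose. The absence of day 15 is a conflict between this assay's sentence, which itself claims similarity to the other assays, and the general timeline. It is not proof that the sample will go unused. That timeline also has an end-of-treatment sample that can fall beyond 180 days. Where rituximab is delayed for a high lymphocyte count (section 6.1), day 29 may not be affected in the same way.

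It is also fair to say that section 11.6 openly recognises B-cell depletion by rituximab, and that isolating lenalidomide is only one of its aims.

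**Conclusion.** The point holds as an internal mismatch in a stated laboratory procedure. As printed, the ELISA measures circulating anti-tetanus antibody, and the 7-day culture contributes nothing to the result. The title and the culture step indicate that production by stimulated cells was the aim, but the text does not settle this.

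Severity is low. This is one exploratory assay in consenting patients, with at most 90 readings. The primary response endpoint, sample size, decision rule and safety monitoring do not depend on it.

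The timing matter is secondary: two statements of the schedule need reconciling, and samples taken after rituximab starts are confounded by B-cell depletion rather than uninformative. The day counts assume 28-day cycles without delay, rituximab on the scheduled days, a day-15 draw before infusion, and 6 months taken as about 180 days.

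**What to change.** 1. State the specimen. If antibody production by stimulated PBMC is the aim, replace serum with the harvested culture supernatant. Add unstimulated-culture and medium-only controls to account for the human serum in the medium.
2. If serum titre is also wanted, describe it as a separate assay and report it under that name. If it is the only readout wanted, delete the culture step.
3. Reconcile the 7-day culture with the 5-day culture it refers back to.
4. Align this assay's times with the timeline in sections 11.5 and 11.6, so that the day-15 lenalidomide-alone sample is used where cell yield allows.
5. State that results from samples taken after rituximab starts are confounded by B-cell depletion and are not to be read as a lenalidomide effect alone.

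The specimen correction is one sentence and uses material already collected. Adding day 15 needs no new draw but costs one more culture per patient, plus the control wells. Whether enough cells remain is uncertain: section 11.5 provides a single 8 mL CPT tube per time, many cell assays compete for PBMC, and no yield is given. An order of priority among the assays would settle which is dropped when cells are short.
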